difficult to “reach” via the usual preventive and intervention strategies due to circumstances of immigration, poverty, and marginalization.

This study will develop and implement a culturally specific, family-based individual, drug use, sexual risk and delinquency risk reduction program for Haitian adolescents aged 13-17 in Miami-Dade County. First, instruments for the intervention will be pretested with 10 Haitian youth and their families and then refined based on cultural acceptability interviews and focus group data. Second, we will conduct a pilot randomized trial with 88 at-risk Haitian youth and their families. We will test the CIFFTA model against the Standard of Care currently being offered by the Miami-Dade’s Juvenile Service Department (JSD) to Haitian adolescents in their diversionary program. The goal of the pilot study is to obtain preliminary data on CIFFTA’s feasibility, cultural acceptability and efficacy.

Research activities will include recruitment of Haitian families whose youths are in the JSD program in Miami-Dade Juvenile Justice System; participant observation in households of recruited families in Miami, Homestead, and Florida City; modification of CIFFTA for use in Haitian families; implementation of a pilot intervention in a limited number of youth and their families; process and outcome evaluation of those interventions; analysis of data resulting from these activities; and design of an intervention to be applied on a larger scale after completion of the present project.

5) Inclusion and Exclusion Criteria*

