This is a multi-wave study, with approximately all the participants recruited by the end of Year 02 and the remainder in the beginning of Year 03. At baseline, we will conduct comprehensive assessments of all study constructs and repeat all other assessments annually. Activities during the first three months will consist of the following: Staffing, Instrument Calibration, Ethnographic Update. Each wave will be composed of 22 participants to be randomized into two groups (11 each). Each undergo assessment at intake (T1) and outtake (T2), a booster session 3 months after outtake and a final assessment at 12 months. Data analysis process will be initiated at the third month and continue throughout the study implementation.

Study Protocol

[figure not shown]
IRB ID: 20180597 (CR00012479)

Study Number: 1 R34 DA043784-01A1

Date: July 19, 2018

Publications are expected to start from month 20. The table below details the activity processes.

Project Timeline

9) Study Endpoints*

Primary outcomes are: intervention attendance and completion; sustained abstinence in substance use through biochemical verification and self-report; family functioning; sexual risk behavior; and conduct disorder.

Secondary outcomes include recidivism in delinquency, improvement in family communication, and peer/gang involvement.

10) Procedures Involved*

RCT procedures

CIFFTA has three major components – Family-Based Therapy, Individual Therapy, and Psycho-educational Modules – delivered over 16 weeks in a six sessions (60 minutes each) per month format. In this study, the therapy will be delivered in the home to reduce missed sessions and premature termination. Special training will focus on how to structure the home environment to reduce distractions. Three sessions per month will typically be a session which may include Family-based Therapy or Psycho-educational modules with the family or parents alone (e.g., parent training). The other three sessions are typically with the adolescent alone and include Motivational Interviewing or Psycho-educational modules designed for the adolescent.

Study Protocol

IRB ID: 20180597 (CR00012479)

Study Number: 1 R34 DA043784-01A1

Date: July 19, 2018

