CIFFTA uses a flexible manual that allows for tailoring of the intervention through the selection of psycho-educational modules that address specific family and adolescent clinical and cultural issues that are central to that lives of that family. Individual and family level targets of change must be specifically able to address the ecological factors as well. For example, parenting practices may be improved to better monitor the adolescent's peers; parental leadership and guidance may focus on taking a more active role in advocacy in schools and in teaching adolescents how to handle racism and discrimination; and adolescent skills may become important in better addressing peer pressure in the peer context.

Overall intervention process.

Study Protocol

IRB ID: 20180597 (CR00012479)

Study Number: 1 R34 DA043784-01A1

Date: July 19, 2018

Pretest. CIFFTA instruments only will be pretested with a subsample of 5 Haitian youths and their families. Youths and families will be selected purposefully and will NOT be included in the study sample. Because the whole trial is consist of testing the applicability of CIFFTA within this population, the study will not be tested prior implementation. The instruments will be tested for fidelity of translation.

Study Process. Randomization will be done after baseline data are logged and will be carried out via computer-generated sequential assignment; in that sense, interventionists do not control randomization and interviewees will be blind to condition. At baseline, we will conduct comprehensive assessments of all study constructs and repeat all other assessments (see timeline). Outcomes anticipated will include lowered risk for re-offending (i.e. YLS scores), rates of recidivism (i.e. re-arrest), drug/alcohol use, and improved psychological adjustment and family functioning of those youths in the intervention group relative to those in the comparison group. Similarly, we expect parents/caregivers of these youths to see improvement in their child's behavior (i.e. less conduct disorder reported) and improved family functioning overall.

Ethnography.

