Youth Urine Toxicology. As part of our research component, we plan to collect voluntary urine specimens for analysis at the times of the youths' initial and follow- up interviews in order to validate self-report. We will follow procedures informed by NIDA's CJDATS workgroup guidelines. Urine specimens will not be collected on youths incarcerated for more than two days. The use of four substances will be probed using the Onsite CupKit® urine screen procedure (positive threshold levels are noted in parentheses): (1) methamphetamines (500 nanograms per milliliter [ng/ml] of urine), (2) opiates (300 ng/ml of urine), (3) cocaine (300ng/ml of urine), and (4) marijuana (THC) (50 ng/ml of urine). The surveillance window for the four drugs is as follows: methamphetamines and opiates = 48 hours; cocaine = 72 hours; marijuana: moderate users = 5 days; heavy users = 10 days; chronic users = 20 days. Although we considered hair analysis, urine screens were selected because of they are the most widely used and accepted method for supervision monitoring (Lipsey & Wilson, 1998), they are minimally invasive, can be collected in the community during follow-up assessments and carry fewer taboos on collection (Meyers et al., 2002). Urine screen results will be kept confidential, and will be collected in containers marked with pre-printed labels without personal identifying information. To assure integrity of the sample, the Onsite CupKit® automatically checks for temperature, and the interviewer will ensure that there is no one else in the restroom.

Overview of Assessment Procedures and Attrition

The 3-month follow-up assessment will be measured from the end of the intervention, as will be the 6-month and the 12-month follow-up

Study Protocol

IRB ID: 20180597 (CR00012479)

Study Number: 1 R34 DA043784-01A1

Date: July 19, 2018

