interviews. All participants entered into the study will be tracked for the follow-up assessments, even if the individual drops out of treatment early. Whereas this is not expected to be a significant problem given the few number of treatment sessions, our design calls for an intent-to-treat assessment and data analytic plan. If the youth or parent cannot be located, records of official agencies (e.g., law enforcement, department of juvenile justice, local jails, department of corrections, state attorney, department of motor vehicles) will be searched. Our tracking efforts will be informed by the successful strategies used by Stouthamer-Loeber et al. (1992), Farrington et al. (1990), and in the Family Empowerment Intervention project (Dembo & Schmeidler, 2002) to minimize attrition. One of the greatest advantages in using family-based approach is that it creates conditions to build relationship over time within the communities studied and with the families. Based on our experiences conducting family-based studies, we will use procedures proven instrumental in obtaining high retention rates.

11) Data and Specimen Banking*

As part of our research component, we plan to collect voluntary urine specimens for analysis at the times of the youths' initial and follow-up interviews in order to validate self-report. We will follow procedures informed by NIDA's CJDATS workgroup guidelines. Urine specimens will not be collected on recruited youths for more than two days.

The use of four substances will be probed using the Onsite CupKit® urine screen procedure (positive threshold levels are noted in parentheses): (1) methamphetamine (500 nanograms per milliliter [ng/ml] of urine), (2) opiates (300 ng/ml of urine), (3) cocaine (300 ng/ml of urine), and (4) marijuana (THC) (50 ng/ml of urine). The surveillance window for the four drugs is as follows: methamphetamine and opiates = 48 hours; cocaine = 72 hours; marijuana: moderate users = 5 days; heavy users = 10 days; chronic users = 20 days.

Although we considered hair analysis, urine screens were selected because of they are the most widely used and accepted method for supervision monitoring (Lipsey

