. The youths to be recruited are minors aged 13-17.

18) Multi-Site Research*

This is not a Multi-Site Research.

19) Community-Based Participatory Research*

This study is not a Community-Based Participatory Research

20) Sharing of Results with Subjects*

Not Applicable.

21) Setting

When a youth is arrested in Miami-Dade, he or she is brought by the arresting officer to the JSD. At the JSD the child goes through an initial arrest process, including fingerprinting, mug shots and other typical intake and assessment procedures. During the intake the youths are asked to self-identify as to their ethnicity. The child is given an assessment which includes a determination of whether or not the appropriate criterion is met for entering a diversion program. Criteria for the various diversionary programs include prior criminal history and the nature of the current arrest. If the child is eligible for a diversionary program then the range and type of programs and services which might be suitable are considered. Programs are offered for substance abuse, educational needs, psychotherapy, family-based interventions, anger management, community service and so forth. If the parents and the youth both agree, then a diversion program is assigned.

Once assignment to a diversion program has been made, participation by the youth, and in many cases also by a parent, becomes a mandatory condition of the program. A case manager is assigned to monitor program compliance. If either fails to participate the program will not be completed and the youth may then be referred to the court system and may face prosecution and further sanctions.

When parents/guardians picking up a project eligible youth meet or when project staff meet eligible youth at the community diversion program, only then will they be informed about their eligibility of the proposed project. Parents/guardians and youths who are interested in participating in the project will then be informed that project services are provided in-home, confidential, and that participation is voluntary. Project's procedures will be performed at the home of the participants in the Haitian neighborhood in Miami-Dade.

22) Resources Available

The PI and Co-Investigators have each at least more than 30 years of large-scale experiences in the field of public health. They have over 3 decades of community-

Study Protocol

IRB ID: 20180597 (CR00012479)

Study Number: 1 R34 DA043784-01A1

Date: July 19, 2018

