### ***Analytic Methods***

Latent Growth Modeling within a Structural Equation Model (SEM) framework. We will conduct latent growth curve analyses using Stata 14 gsem (1), SAS Proc Mixed (2), SPSS Mixed Models, and/or Mplus 8 (3) to compare the trajectories of participants in CIFFTA to those in TAU. Given that the data are balanced and have more than 2 time points, the model is identified, thereby allowing us to perform SEM growth curve analysis (4). These models conceptualize each component of growth (the baseline/intercept, the slope/rate of change, the quadratic slope, etc.) as composed of a fixed and random effect. Thus, these models have multiple components of variance as well as a regression-type model of the underlying mean growth curves of the two groups. Within an SEM framework, growth curves are treated as latent (unobserved) variables influenced by occasion- and individual-level covariates, allowing us to explicitly model growth trajectories overtime.

Specific analysis link functions will be matched to fit the distribution of each outcome variable. For ordinal outcomes (e.g., frequency of drug/alcohol usage), we will use an ordinal logistic regression function. The proportional odds assumption will be evaluated using the Brant test, and if needed, addressed by allowing problematic coefficients to vary across levels of the outcome variable. Count outcome measures (e.g., number of sexual partners, problem behaviors, re-arrests) will be analyzed using a negative binomial function rather than Poisson regression to address potential over-dispersion. Vuong tests will be performed to assess whether the data have an excess of zeros, and if necessary, zero inflated negative binomial regression will be used instead.

Analysis for Aims 2 and 3: The first set of analyses will explore the efficacy of CIFFTA compared to SOC in modifying the main adolescent outcomes and to generate effect sizes for a possible full clinical trial: a) drug/alcohol use, b) risky sexual behavior, c) delinquent behavior, and d) recidivism. Latent growth modeling will be used to investigate the efficacy of CIFFTA as compared to SOC. For each model, we will examine the effect sizes to determine the overall impact of CIFFTA over SOC on the outcome variables. We will generate estimates of effect sizes, such as Cohen's d (5), for both rate of change and for the

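### The 3-, 6- and 12-month follow-ups are timed from an end of intervention that is defined only for CIFFTA completers, so equal time since randomisation in the two arms is not assured

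*Protocol*

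**What the plan says.** **Visit clock.** Protocol section 10, in its overview of assessments and attrition, sets the rule for the interviews: "The 3-month follow-up assessment will be measured from the end of the intervention, as will be the 6-month and the 12-month follow-up".

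**Randomisation.** Protocol section 10 (Study Process): "Randomization will be done after baseline data are logged". The end of any intervention therefore comes after allocation.

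**Length of treatment.** CIFFTA is "delivered over 16 weeks in a six sessions (60 minutes each) per month format" (Protocol section 10, RCT procedures). For the comparator, Protocol section 4 says: "We will test the CIFFTA model against the Standard of Care currently being offered by the" county's juvenile services department. Protocol section 21 describes a mixture of diversion services: "Programs are offered for substance abuse, educational needs, psychotherapy, family-based interventions, anger management, community service and so forth". No length or end point is given for any of them.

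**Early leavers.** "All participants entered into the study will be tracked for the follow-up assessments, even if the individual drops out of treatment early", and "our design calls for an intent-to-treat assessment and data analytic plan" (both Protocol section 10). Neither sentence says which date counts as the end of the intervention for a youth who stops early.

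**Analysis.** SAP, Analytic Methods: "Given that the data are balanced and have more than 2 time points, the model is identified". The SAP then plans effect sizes for the rate of change and for the between-arm difference at a given time, and separate hazard analyses of the period after the intervention. It states no time origin, visit window or time scores.

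**The concern.** In a randomised comparison the clock should start at allocation, or at a date fixed by it, so that both arms are seen at the same elapsed time whatever happens in treatment. Here it starts at an event that can depend on the arm and on the youth's behaviour. Protocol section 21 says that failure to participate leaves the diversion programme uncompleted and may lead to court referral. The end of standard of care could thus be linked to the delinquency outcomes. Early exit from CIFFTA is also unlikely to be random.

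If the end dates did differ, the same nominal visit would fall at different elapsed times in the two arms. An outcome that changes over time in everyone could then show a between-arm difference in slope or level with no treatment effect. The trial is meant to supply effect sizes for planning a full trial (SAP, analysis for Aims 2 and 3), so such a difference could carry forward. The hazard analyses share this origin, because they begin when the intervention ends.

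**Working it through.** The plan gives no figure for time since randomisation, so there is none to reproduce. The check sets out what the stated rule implies.

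**Inputs from the documents.** CIFFTA lasts 16 weeks. Follow-ups come 3, 6 and 12 months after the end of the intervention, taken as 13, 26 and 52 weeks. The SAP intends to analyse 80 participants, so 40 per arm under the equal split in Protocol section 8.

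**Assumptions.** Treatment starts at randomisation. Standard of care lasts 8 to 24 weeks. One early leaver stops CIFFTA at week 4.

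**Formula.** Week of visit since randomisation = week in which the intervention is taken to end + nominal follow-up in weeks.

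| Case | End | 3-month | 6-month | 12-month |
|---|---|---|---|---|
| CIFFTA, completed | 16 | 29 | 42 | 68 |
| Standard of care, 8 weeks (assumed) | 8 | 21 | 34 | 60 |
| Standard of care, 16 weeks (assumed) | 16 | 29 | 42 | 68 |
| Standard of care, 24 weeks (assumed) | 24 | 37 | 50 | 76 |
| CIFFTA, left at week 4, actual stop date used | 4 | 17 | 30 | 56 |
| CIFFTA, left at week 4, planned end used | 16 | 29 | 42 | 68 |

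The rule can therefore give no gap, or a gap of 8 weeks either way between completers within the assumed range. The early leaver is seen 12 weeks sooner (68 − 56) or not sooner at all, depending on which date is meant.

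**Counts accrued since randomisation.** At a constant event rate with no treatment effect, the expected ratio of standard of care to CIFFTA is the ratio of elapsed times. At the 12-month visit this is 60/68 = 0.88 to 76/68 = 1.12. For an item with a fixed recall window the exposure is the same in both arms, and the ratio is 1.00.

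**Outcomes that drift with time.** Eight weeks is 8/4.348 = 1.84 months. With a common drift of s SD per month, the spurious standardised difference is d = 1.84 × s. With 40 per arm its standard error is √(2/40) = 0.224. The two-sided type I error at a nominal 0.05 for one follow-up contrast is then:

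| s (assumed) | Spurious d | Type I error |
|---|---|---|
| 0.02 | 0.04 | 0.053 |
| 0.05 | 0.09 | 0.07 |
| 0.10 | 0.18 | 0.13 |

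These values illustrate the mechanism. Neither the gap nor the drift is known.

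**The schedules side by side.**
- Protocol section 3: 3, 6 and 12 months, with no origin.
- Protocol section 8: annual repeats in one sentence; intake, outtake and a final assessment at 12 months in another, with no origin for the 12 months.
- Protocol section 10, Instrumentation: the Conduct Disorder Subscale, which measures a primary outcome, at intake and termination only.
- Protocol section 10, Overview of Assessment Procedures: 3, 6 and 12 months from the end of the intervention.

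The time origin cannot be settled by reading these together.

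**The case against.** The strongest reply is that no difference between the arms has been shown. Standard of care may also end at 16 weeks. Protocol section 8 describes one schedule for both groups of a wave, and the SAP (Analysis Rationale) says that each of the four waves has its own start and finish. A finish date common to the wave would remove the confounding. For early leavers, the planned end fits the intent-to-treat wording at least as well as the personal stop date. All of this stands. A reader might infer that the arms will be assessed at different times, or that dropouts will be seen earlier; the documents support neither as fact.

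A reader might also infer that the growth model treats all visits with the same label as simultaneous. The SAP does not say so. It uses the word balanced to argue identification, which may mean only an equal number of occasions, and it names mixed-model software that can take actual times. What remains is that no time scores are specified, and an equal number of occasions would not by itself justify common ones.

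Nor should the ratios of 0.88 to 1.12 be read as the expected bias in the planned counts. No passage defines counts as accruing from randomisation, and the drug-use interview (Protocol section 10, Instrumentation) uses recall windows of 30 days and of 3, 6 and 12 months.

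The Cox model does handle unequal length of follow-up through censoring. It does not correct a starting point that may differ between arms.

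Finally, follow-up after treatment is a reasonable choice when sustained abstinence is a primary outcome, and a randomisation clock gives up some of that. The project timeline in Protocol section 8 and an opening part of the SAP were not available to read, and either may fix dates. These points limit the claim to what is undefined in the available text.

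**Conclusion.** The point holds as a gap in definition. Follow-up is anchored to a post-randomisation event that has a stated length only for CIFFTA and no defined date for standard of care or for early leavers. Following the plan as written does not assure equal time since randomisation, and the claim of balanced data is unsupported for slopes and time-specific differences.

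The size cannot be derived from the documents. It is zero with a 16-week standard of care (for completers) or a common planned end date. Under the assumed 8 to 24 weeks, the 12-month visit would be up to 8 weeks earlier or later than in CIFFTA. Any effect would be confined to outcomes that drift with time and to counts accrued since randomisation. In a pilot that the SAP itself calls preliminary, this does not undermine the trial, but it is worth settling because the remedy is simple.

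**What to change.** 1. Time the outtake and follow-up assessments from randomisation in both arms, for example at 16 weeks and then at 16 weeks plus 3, 6 and 12 months, whether or not treatment has ended or was stopped early. State the same visit windows for both arms.
2. In the SAP, name randomisation as the time origin. Use actual time since randomisation in the growth and survival models, and an exposure offset for any count accrued since randomisation. Items with fixed recall windows need no offset.
3. Reconcile the assessment schedules in Protocol sections 3, 8 and 10, including the two occasions given for the Conduct Disorder Subscale.

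This is a cheap improvement: protocol and SAP wording, the same number of follow-up visits and no change in sample size. The downside is that some standard-of-care youths would be assessed before or after their programme ends, so for them the visits are no longer strictly post-treatment. If standard of care ran 24 weeks, for instance, the 16-week visit would come 8 weeks before its end. Recording each youth's actual end of treatment would let that be described.

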& Wilson, 1998), they are minimally invasive, can be collected in the community during follow-up assessments and carry fewer taboos on collection (Meyers et al., 2002). Urine screen results will be kept confidential in containers marked with pre-printed labels without personal identifying information. To assure integrity of the sample, the Onsite CupKit® automatically checks for temperature, and the interviewer will ensure that there is no one else in the restroom.

Study Protocol

IRB ID: 20180597 (CR00012479)

Study Number: 1 R34 DA043784-01A1

Date: July 19, 2018

12) Data Management*

Qualitative data:

Research staff will be monitored during every step of data collection by appropriate investigators. Instruments will be reviewed periodically to insure validity and reliability. Data will be entered by our personnel into a database under the supervision of PI. Control measures will be instituted to ensure accuracy of data entry procedures prior to analysis. Also, all data will be analyzed at our data processing center, under guidelines of our data safety and monitoring plan. All written and tape-recorded materials in this study will be transcribed using Microsoft Word on a daily basis and stored in locked the PI files cabinet. They will be coded and analyzed using procedures described in Schensul et. al.

The PI, with the assistance of the project's co-Is and Post-Doctoral Associate, will analyze the data using SPSS®, STATA®, the R statistical package or relate statistical software. Outcome measures will include drug use, delinquency/crime, family functioning, educational performance, and emotional/ psychological functioning. Predictor and outcome data will be analyzed using confirmatory factor analysis, generalized linear mixed effects modeling, latent growth modeling, structural equation modeling, analysis of variance, logistic regression, and stepwise multiple regression. The significance levels will be adjusted to control for multiple outcome measures. For the primary hypotheses, power is anticipated to be .80.

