**Power Analysis:** We will recruit 88 participants for this study, with the intention of analyzing data for 80 participants after attrition. The original CIFFTA randomized trial with 28 Hispanic adolescents showed CIFFTA to be more efficacious than the comparison family treatment at: 1) reducing drug use, and 2) improving parenting practices as reported by adolescents (7). More recently, a technology assisted CIFFTA study of 80 minority youth at high risk for drug use showed CIFFTA to be more efficacious in reducing behavior and conduct problems and in improving family cohesion, when compared to a delay treatment condition (8). Based on these findings, CIFFTA was placed on the National Registry of Evidence Based Practices using their more rigorous criteria for entry. Given such consistent findings of efficacy for CIFFTA among Hispanic youth, a sample size of 80 will be sufficiently powerful to detect relatively small effects ( $R^2 = 0.05$ ) at adequate levels of power (0.84 - 0.86) using a relatively simple SEM. A sample size of 80 is also well above sample guidelines for Stage 1 treatment trials (80)). Nevertheless, to deal with attrition, which in the case of Haitian and because of the ethnographer's engagement with the families will not be higher than 10%, we plan a sample of 88 adolescents.

Nevertheless, we recognize and appreciate the limits of estimating simple SEMs, such as ours, with a small sample size. Therefore, we will take several steps to mitigate concerns about statistical power, including: limiting the use of latent variables when possible, constructing parsimonious path models, and using Bayesian estimators. When theoretically and empirically appropriate, we will use principal components factor analysis to combine multiple indicators into a single scale capturing the underlying construct rather than estimating multiple latent variables since the latter often requires larger samples.

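### The protocol promises significance levels adjusted for multiple outcomes, but the SAP names no adjustment, family or alpha, and its stated power of 0.84-0.86 is not tied to an adjusted level and cannot hold at one.

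*Protocol*

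**What the plan says.** **Protocol.** Section 12 (Data Management) commits without qualification: "The significance levels will be adjusted to control for multiple outcome measures". The next sentence reads: "For the primary hypotheses, power is anticipated to be .80". No alpha, sidedness, method, family of tests or effect size is attached to either. Section 9 (Study Endpoints) opens "Primary outcomes are: intervention attendance and completion" and goes on to abstinence from substance use, family functioning, sexual risk behaviour and conduct disorder. That makes five primary domains, with three secondary ones after them.

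**SAP.** Analytic Methods names four main adolescent outcomes for the growth models: drug/alcohol use, risky sexual behaviour, delinquent behaviour and recidivism. It then adds mediation paths through three named mediators and several hazard-rate comparisons. The Power Analysis says: "We will recruit 88 participants for this study, with the intention of analyzing data for 80 participants after attrition". It claims to detect an R-squared of 0.05 "at adequate levels of power (0.84 - 0.86) using a relatively simple SEM". No significance level is given there or elsewhere in the SAP text read here, which runs from Major Analytic Methods Proposed to the references. The steps offered to protect power are fewer latent variables, sparse path models and Bayesian estimators. None of them deals with multiple outcomes.

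**The concern.** An analyst who works from the SAP has nothing with which to carry out the protocol's commitment: no list of tests to adjust across, no level to share between them and no procedure. If each outcome is tested at a conventional level, the promised error control is not delivered. If the adjustment is applied, each test becomes stricter, and a power figure quoted without a level no longer describes the design. The results are meant to show initial efficacy and to help justify a full trial. Both a chance finding on one of several outcomes and an overstated chance of detecting a real effect would feed into that decision. If the family and method are chosen after outcome data are seen, the promised control loses its meaning.

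**Working it through.** **Inputs**
- 80 analysed, R-squared 0.05, power 0.84-0.86: SAP, Power Analysis.
- 1:1 allocation: Protocol section 8 (11 and 11 per wave), hence 40 v 40.
- Number of outcomes m: 5 (Protocol section 9) or 4 (SAP, Analytic Methods).
- Assumed, because the documents are silent: two-sided 0.05 before adjustment, and Bonferroni as the reference method. This gives 0.05/4 = 0.0125 and 0.05/5 = 0.01.

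**Step 1. The SAP's own power figure.** For a one-df test, f² = R²/(1 - R²) = 0.05/0.95 = 0.0526, which at 1:1 is d = 2√0.0526 = 0.46. The noncentrality is 80 × 0.0526 = 4.21, referred to F with 1 and 78 df. Power at two-sided 0.05 is **0.53**, not 0.84-0.86. At one-sided 0.05 it is 0.65. Reaching 0.84-0.86 at two-sided 0.05 would take about 168-178 analysed, or an R-squared of about 0.10-0.11 with 80.

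**Step 2. The same inputs at an adjusted level.**

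| Level | Power, N = 80, R² = 0.05 |
|---|---|
| 0.05 | 0.53 |
| 0.0125 (m = 4) | 0.31 |
| 0.01 (m = 5) | 0.29 |

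**Step 3. Taking the stated powers as true at two-sided 0.05.** Adjusted power = Φ(z₀.₉₇₅ + z_power - z₁₋α/₂ₘ), with α = 0.05 and critical values 2.498 (m = 4) and 2.576 (m = 5). For 0.84, z₀.₉₇₅ + z_power = 1.960 + 0.994 = 2.954, so m = 5 gives Φ(2.954 - 2.576) = Φ(0.378) = 0.65.

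| Stated power | m = 4 | m = 5 |
|---|---|---|
| 0.80 (protocol) | 0.62 | 0.59 |
| 0.84 (SAP) | 0.68 | 0.65 |
| 0.86 (SAP) | 0.71 | 0.68 |

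Holm loses less when several outcomes respond. Simulated with every outcome carrying the stated effect (400,000 draws, correlation 0 to 0.5), average power per outcome for the SAP's 0.84-0.86 is about 0.75-0.81 over m = 4 and 5. That is still below the stated range.

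**Step 4. No adjustment.** With independent true nulls, the chance of at least one false positive is 1 - 0.95^m: 0.185 for four and 0.226 for five. Simulated at correlation 0.5, it is 0.16 and 0.18. The range is about 16-23%, or three to four and a half times 0.05.

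**Step 5. Effect detectable at 80% power, 40 v 40.**

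| Level | d | R² |
|---|---|---|
| 0.05 | 0.63 | 0.09 |
| 0.0125 | 0.76 | 0.13 |
| 0.01 | 0.78 | 0.13 |

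About half the distance from the SAP's 0.05 to 0.13 is there before any adjustment. It belongs to the failure to reproduce in step 1; multiplicity accounts for the rest.

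**The case against.** **No alpha is stated, so no stated error rate is wrong.** This stands. The protocol offers a promise of control, not a figure, and every percentage above rests on the assumed two-sided 0.05.

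**The protocol's .80 may already be after adjustment.** A reader might infer that .80 is overstated. The documents do not support this: the figure directly follows the adjustment sentence and carries no effect size or alpha. The fall to 0.59-0.62 is conditional on its having been meant at unadjusted 0.05. The same defence does not rescue the SAP's figure, because its stated inputs give only 0.53 before adjustment on a simple test.

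**Silence is not contradiction.** A reader might infer that the SAP overrides the protocol and tests unadjusted. It never says so, and the two documents can be followed together. What is established is that the SAP supplies no means of carrying out the rule.

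**The family may not be five.** The SAP describes no between-arm test of attendance and completion, and its own list has four outcomes. This stands, and it is why both counts are shown. The conclusion is the same for either.

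**A richer model could have more power.** With covariates (four predictors), an R-squared increment of 0.05 reaches 0.84 if the whole model explains about 55% of the variance. The SAP does not claim this, and power would then still fall to 0.66 (four outcomes) or 0.63 (five) under Bonferroni.

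**It is a pilot.** The SAP calls its analyses preliminary and intends to generate effect sizes, which limits the severity. But it also tests hypotheses and path significance and quotes power, and nothing withdraws the protocol's commitment.

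**Conclusion.** The point holds as a commitment that the SAP does not carry out, together with a SAP power claim that the design does not deliver at any adjusted level. The adjusted power is about 0.29-0.31 on the SAP's own inputs with a simple one-df test. If 0.84-0.86 is granted at two-sided 0.05, it is about 0.65-0.71 under Bonferroni, and higher under Holm if several outcomes respond. Without adjustment, the chance of at least one false positive is about 16-23%.

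These sizes rest on two-sided 0.05, four or five between-arm outcomes, and correlation between 0 and 0.5. A reader might take 0.65-0.68 as the true adjusted power for five outcomes. It is not: it carries forward a figure that does not reproduce. Because the analyses are described as preliminary, this is something that should be fixed, not a defect that invalidates the trial.

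**What to change.** In the SAP:
- Name the primary outcomes that are compared between arms, with one contrast each.
- State the alpha, its sidedness and the method, for example Holm.
- State whether the mediation, hazard and secondary tests belong to that family or are exploratory.

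In Protocol section 12 and the SAP's Power Analysis, recompute power at the adjusted level from a stated effect size. Report the effect detectable at 80% power: about d = 0.76-0.78 (R-squared 0.13) for 40 v 40 at 0.0125-0.01. Do not insert 0.65-0.68 as the power.

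Alternatively, if the pilot is for estimation only, say so in both documents, report estimates with intervals, and remove the adjustment promise and the power claims.

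Either route should be settled before outcome data are seen. The cost is wording, a recalculation and, if power is kept, a less favourable figure. No extra participants are needed.
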